2.5. Sample Size Determination

A total sample size of approximately 480 subjects (approximately 120 per treatment group, randomized in a 1:1:1:1 ratio) is estimated to provide 80% power to detect a reduction in odds of 66% between each GB001 group and placebo at an 0.050 two-sided level of significance for the primary endpoint of the proportion of subjects who experience worsening of asthma by Week 24. This assumes the proportion of subjects who experience worsening of asthma by Week 24 is 25% in the placebo group and 10.2% in each GB001 group and a dropout rate of 8%.

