8.3. Analysis Methods

8.3.1. Primary Efficacy Analyses

The primary endpoint is the proportion of subjects who experience worsening of asthma by Week 24 as defined by at least one of the following:

- On 2 consecutive days, AM PEF \leq 75% of mean AM PEF measured over the last 7 days of the Run-in
- $FEV_1 < 80\%$ of baseline (Visit 2)
- Increase in rescue medication use of ≥ 6 puffs/day on 2 consecutive days compared to mean use over the last 7 days of the Run-in
- Increase in ACQ-5 score of ≥ 0.5 compared to baseline (Visit 2)
- The occurrence of a severe asthma exacerbation (asthma attack) defined as deterioration of asthma that leads to the use of systemic corticosteroids for at least 3 days, hospitalization, or an Emergency Department visit

Logistic regression modeling will be used to compare each GB001 group with placebo. The model will include covariates for treatment group, ICS dose (medium or high) at randomization, region (North America, Eastern Europe, Western Europe), baseline pre-bronchodilator FEV₁, and baseline ACQ-5 score. If the full model does not converge, a model with treatment group, ICS dose at randomization, and region as covariates will be utilized. If this reduced model does not converge, a model with treatment group and ICS dose at randomization will be used. In the rare case that convergence issues remain, only treatment group will be included in the model.

The number and proportion of subjects meeting the primary endpoint and corresponding 95% Wilson (Score) CIs (Wilson, 1927) will be summarized by treatment group. ORs, corresponding asymptotic 95% CIs along with the absolute differences and corresponding 95% CIs, and p-values will be summarized for each GB001 group versus placebo. The 95% CIs for the absolute difference will be Newcombe continuity-corrected CIs (Newcombe, 1998). Percentage reductions and corresponding 95% CIs will also be summarized. Lastly, the number and proportion of subjects meeting each component of the primary endpoint, with observed worsening of asthma, and with an assigned status of asthma worsening will also be summarized by treatment group. Subjects can meet more than one component of the primary endpoint.

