8.3.1.1.4. Sensitivity Analysis #4: Multiple Imputation

If the number of subjects overall with a missing observed status for asthma worsening by Week 24 is \geq 5%, then the following MI approach will be conducted as a sensitivity analysis.

The dichotomous outcome of asthma worsening by Week 24 will be imputed for subjects who have withdrawn from study without having experienced asthma worsening using a MI approach assuming that these subjects with a missing dichotomous outcome would have similar outcomes to subjects who had an observed status of asthma worsening by Week 24. The dichotomous outcome will be imputed directly as opposed to imputing the individual components of the primary endpoint and then deriving the composite outcome.

The following steps will be performed:

- Intermittent missing values will first be imputed using the Fully Conditional Specification method, which is appropriate for non-monotonic missing data for binary data.
- The monotone missing values will then be multiply imputed using the monotone logistic regression imputation method (Allison, 2005). A monotone missing pattern is such that in the event that a variable is missing it is implied that all subsequent variables are also missing (i.e. once a subject withdraws from study, no additional data is expected for that subject).
- For each stage, MI will be performed within treatment group with covariate adjustment the same as the primary analysis of the primary endpoint and non-missing outcomes for asthma worsening. Should convergence issues occur due to small cell size for the categorical covariates at either stage, they will be removed from the model.
- The primary analysis of the primary endpoint as described in Section 8.3.1 will be performed for each complete, imputed dataset.
- Fifty imputations will be performed.
- Results of the logistic regression on the multiple imputed data sets will be combined to generate an overall estimate and associated variance using Rubin's rules (Rubin, 1987).

The imputed data logistic regression model-based estimates of the proportion of subjects with asthma worsening, ORs, corresponding 95% CIs, and p-values will be reported. Percentage reductions and corresponding 95% CIs will also be provided.

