8.3.2.1. Change from Baseline to Week 24 Endpoints

Change from baseline to Week 24 in ACQ-5 score, pre-bronchodilator FEV₁, postbronchodilator FEV₁, and AM PEF will be analyzed as described below. The ACQ-5 is a five-item questionnaire which has been developed as a measure of the subject's asthma control that can be quickly and easily completed (Juniper E. F., 2005). The response options for each of these questions consists of a zero (no impairment/limitation) to 6 (total impairment/limitation) scale with the total score ranging from 0 to 30. ACQ-5 score is the average of the 5 non-missing items and will be calculated at each visit for each subject. The minimal clinically important difference (MCID) is 0.5 points.

For AM PEF, the baseline value is defined as the mean over the last 7 days of the Run-in including the value on Day 1 and Week 24 is defined as the mean over the last 7 days prior to Week 24 including the value on the day of the Week 24 visit. For the other endpoints, the baseline value is defined as the last non-missing value on or before the date of the first dose of study treatment.

If the number of subjects overall with a missing change from baseline value is < 5% for a particular endpoint:

- The primary analysis will be analysis of covariance (ANCOVA) without MI.
- As a sensitivity analysis, mixed-effects model with repeated measures (MMRM) without MI will also be performed.

If the number of subjects overall with a missing change from baseline value is \geq 5% for a particular endpoint:

- The primary analysis will be ANCOVA with MI.
- As sensitivity analyses, MMRM with MI, ANCOVA without MI, and MMRM without MI will also be performed.

Post-bronchodilator FEV_1 will not be analyzed using MMRM as it is collected at only one post-baseline timepoint.

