Each secondary endpoint of change from baseline to Week 24 will be analyzed using ANCOVA models. For this analysis, the MI procedure analogous to that described in Section 8.3.1.1.4 will be performed if the number of subjects overall with a missing change from baseline value is \geq 5% with the following modifications for cts data: (1) intermittent missing values will be imputed using the Markov Chain Monte Carlo (MCMC) method (Schafer, 1997), and (2) monotone missing values will be imputed using a regression model. Covariate adjustment will be the same as for the primary endpoint for ACQ-5 score and pre-bronchodilator FEV₁. For postbronchodilator FEV₁ and AM PEF, the covariates used in the model will be the same as for the primary endpoint except that baseline pre-bronchodilator FEV₁ will be replaced with baseline post-bronchodilator FEV₁ or baseline AM PEF, depending on the endpoint of interest. ANCOVA without MI will be performed similarly as described above without the imputation of values.

Descriptive statistics for change from baseline to Week 24 along with the LS means, SEs, and corresponding 95% CIs for each treatment group will be presented. Differences in LS means, SEs, corresponding 95% CIs, and p-values for each GB001 group versus placebo will also be constructed from the ANCOVA models.

In addition, each secondary endpoint of change from baseline to Week 24 will be analyzed by MMRM except for change from baseline to Week 24 in post-bronchodilator FEV₁. MMRM will

be performed using a restricted maximum-likelihood (REML)-based approach and an unstructured covariance structure to model within-subject error. The MMRM model will include change from baseline values up to Week 24 as the response variable; the fixed, categorical effects of treatment group, ICS dose (medium or high) at randomization, region, visit, and treatment group by visit interaction; and the cts, fixed covariates of baseline value and baseline value by visit interaction.

Parameters will be estimated using REML with the Newton-Raphson algorithm. Treatment comparisons will be derived from the MMRM. Differences in LS mean changes from baseline, the corresponding 95% CIs, and p-values with Kenward-Roger adjustment (Kenward, 1997) will be provided for comparison for each GB001 group versus placebo. LS means will be reported along with SEs and corresponding 95% CIs, and differences between treatment groups reported with LS means, SEs, corresponding 95% CIs, and p-values.

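### For post-bronchodilator FEV1, the primary multiple imputation draws on essentially the ANCOVA's own baseline covariates, so it adds almost nothing to the complete-case ANCOVA that is its only sensitivity analysis

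*SAP*

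**What the plan says.** SAP 8.3.2.1 sets two branches by the overall share of missing changes. Below 5%, ANCOVA without MI is primary. At 5% or more, "The primary analysis will be ANCOVA with MI". For post-bronchodilator FEV1, SAP Table 1 then leaves ANCOVA without MI as the only sensitivity analysis, because the endpoint "will not be analyzed using MMRM as it is collected at only one post-baseline timepoint".

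The imputation is described by analogy with SAP 8.3.1.1.4, which imputes within treatment group, with covariate adjustment "the same as the primary analysis of the primary endpoint and non-missing outcomes for asthma worsening". For continuous endpoints, intermittent gaps are filled by MCMC, and "monotone missing values will be imputed using a regression model".

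The primary model in SAP 8.3.1 is stated as "The model will include covariates for treatment group, ICS dose (medium or high) at randomization, region", plus baseline pre-bronchodilator FEV1 and baseline ACQ-5. For post-bronchodilator FEV1, "the covariates used in the model will be the same as for the primary endpoint except that baseline pre-bronchodilator" FEV1 gives way to baseline post-bronchodilator FEV1. No post-baseline variable is named.

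Protocol 8.1.3 and the Schedule of Activities place pre-bronchodilator spirometry at Weeks 4, 8, 12, 16, 20 and 24. Post-bronchodilator FEV1 is taken at Screening and then at Week 24 or the Early Discontinuation of IP visit.

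**The concern.** Imputing an outcome from the same covariates that the analysis model already holds adds random noise but no information about the missing subjects. The primary and the sensitivity analysis then rest on nearly the same missing-data assumption. Their agreement would look like robustness in the study report but would test very little.

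The other three change endpoints (ACQ-5, pre-bronchodilator FEV1, AM PEF) have earlier visits to feed the imputation, and MMRM besides. Post-bronchodilator FEV1 has neither, although a closely related measurement is taken at five visits between randomization and Week 24. Lack of efficacy is a listed reason for withdrawal (Protocol 7.2), so dropout related to the lung-function course is plausible, and these visits carry the information that could address it.

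**Working it through.** **The plan's own figure.** The plan states no number for this endpoint. Its only computed figure is the power for the primary endpoint, used here because it carries the dropout assumption: "10.2% in each GB001 group and a dropout rate of 8" per cent. Evaluable per arm: 120 × 0.92 = 110.4. Odds ratio: (0.102/0.898)/(0.25/0.75) = 0.341, log -1.077. Standard error: √[1/(110.4 × 0.25 × 0.75) + 1/(110.4 × 0.102 × 0.898)] = 0.384. Power: Φ(1.077/0.384 - 1.96) = 80.1%. The stated 80% is reproduced.

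**Which branch applies.** The threshold is 0.05 × 480 = 24 subjects. If each subject is missing with probability 0.08, the binomial chance of 24 or more is 99.6%. That takes every dropout as missing. If half of them have an Early Discontinuation of IP value that counts as Week 24 (an assumption), missingness is 4% and the chance is 16%; if 60% do, missingness is 3.2% and the chance is 2%.

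**What the imputation model holds.** Within arm: ICS dose, region, baseline ACQ-5 and baseline post-bronchodilator FEV1. These are the ANCOVA covariates. With a single post-baseline time point there is no earlier outcome to add.

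**Simulation.** Four arms of 120, 50 imputations by Bayesian regression within arm, Rubin's rules, and the SAP's ANCOVA; 200 trials per scenario. Assumptions not in the documents: true difference 100 mL, residual SD 350 mL, correlation r between the last pre-bronchodilator change and the Week 24 post-bronchodilator change, and placebo dropout rising by k log-odds per SD of poor course, with random dropout on GB001. Bias against the full-data estimate at 8% dropout, in mL:

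| k | r | ANCOVA without MI | MI as specified | MI with pre-bronchodilator FEV1 |
|---|---|---|---|---|
| 1 | 0.6 | -16.2 | -16.3 | -0.8 |
| 1 | 0.8 | -21.8 | -22.1 | -0.6 |
| 2 | 0.6 | -23.4 | -23.5 | +0.7 |
| 2 | 0.8 | -32.2 | -32.0 | -0.2 |

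A separate simulation (400 trials per scenario; r = 0.5, 0.7, 0.85) gave -15, -24 and -29 mL for both planned analyses, and +1, -2 and -1 mL with pre-bronchodilator FEV1 added.

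**Scale.** The standard error is about 350 × √(2/110.4) = 47 mL. The simulated values were 46.9-47.0 mL without MI and 47.2-47.3 mL with MI. The bias is therefore 15/47 = 0.3 to 32/47 = 0.7 standard errors. Within a trial the two planned estimates differ by about 3 mL (root mean square) and correlate at about 0.998.

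**Where the result changes.**
- Dropout tied only to baseline covariates, common slopes: both analyses are essentially unbiased; at 8% dropout they differ within a trial by about 6 mL (root mean square).
- Dropout tied to baseline, with a deliberately large slope difference between arms: at 8% dropout, ANCOVA without MI averages 105.6 mL and MI 97.8 mL, against 98.5 mL with full data, a gap of about 8 mL in favour of MI. At 20% dropout the gap is 119.0 - 102.0 = 17 mL.
- Worsening status added as a predictor, the literal reading of SAP 8.3.1.1.4: at 8% dropout the bias falls from -16.3, -22.1, -23.5 and -32.0 to -14.2, -19.8, -20.3 and -28.4 mL, a reduction of 10% to 14%.
- Random dropout in all arms: the only gain from adding pre-bronchodilator FEV1 is a 1-3% smaller standard error.

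**The case against.** The strongest objection is the Early Discontinuation of IP value. Subjects who stop treatment and withdraw together are to have that visit's procedures (Protocol 7.1 and 7.2), which include post-bronchodilator spirometry. SAP 3.1 assigns visits by actual day in windows without gaps. If windows are built separately for each parameter, Week 24 is the only post-bronchodilator window and could absorb an early value. SAP 3.1 does not settle this. The objection stands to this extent: the MI branch is likely, not certain. Below 5%, however, ANCOVA without MI is primary and has the same limitation.

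Second, the content of the imputation model is inferred. The SAP says only that the procedure is analogous, and the covariate swap appears in a paragraph about the ANCOVA. That is fair, but the worsening-status reading changes little.

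Third, a reader might infer that liver-related stops on GB001 and efficacy failures on placebo will make dropout differ by arm. The documents do not support this. Stopping treatment is not leaving the study: Protocol 7.1 and Appendix 6 keep such subjects in follow-up, and Protocol 6.4 allows background therapy to be adjusted after worsening.

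Fourth, the bias figures come from an assumed one-sided mechanism, and the near-zero bias after the fix is expected when dropout is generated from the course that the fix adds. In that scenario the bias runs against GB001, so it is not a false-positive risk.

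**Conclusion.** The point holds with limits. If the 5% threshold is reached, ANCOVA with MI for post-bronchodilator FEV1 carries almost no information beyond ANCOVA without MI, and comparing the two is a weak sensitivity analysis. This follows from the model structure and does not depend on the assumed values, apart from slope differences between arms.

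Two stronger readings are tempting. One is that the two analyses are identical. They agree only up to imputation noise, and within-arm imputation can do better when slopes differ. The other is that the endpoint has no valid handling of dropout. Both analyses already deal with dropout explained by ICS dose, region, baseline ACQ-5 and baseline post-bronchodilator FEV1; what is missing is correction for dropout related to the post-baseline course.

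The size, about -15 to -32 mL or 0.3 to 0.7 standard errors at 8% missing, is conditional on the assumed effect, SD, correlation and dropout mechanism. It is not a forecast. Priority is modest: no primary conclusion depends on this endpoint, and pre-bronchodilator FEV1, with repeated values and MMRM, is the lung-function measure chosen for the dose-response and subgroup analyses.

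**What to change.** In SAP 8.3.2.1, state that the imputation model for Week 24 post-bronchodilator FEV1 includes baseline and all available post-baseline pre-bronchodilator FEV1 values as auxiliary variables. Leave the ANCOVA unchanged. ANCOVA without MI then becomes an informative comparison.

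In the same place, state whether a post-bronchodilator value from the Early Discontinuation of IP visit enters the imputation model as a predictor rather than standing in for the Week 24 value. This also settles how the 5% rule is counted.

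The cost is two sentences, slightly more programming and a larger imputation model. No new data are needed. Blinded staff should make the change before the final unblinding.

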If a given analysis fails to converge due to the complexity of model specification, the following will be considered to enable model convergence: 1) use of maximum likelihood estimation instead of REML; and/or 2) a compound symmetric or first-order autoregressive covariance structure will be utilized, based on the covariance structure converging to better fit as determined based on Akaike's information criterion (Akaike, 1973).

Actual values and change from baseline values for ACQ-5 score, pre-bronchodilator FEV₁, postbronchodilator FEV₁, and AM PEF will be summarized by visit. Differences in means, SEs, and corresponding 95% CIs constructed from analysis of variance (ANOVA) models adjusting for treatment group only will also be presented. In addition, figures of mean actual values and mean change from baseline values, including SE bars, for ACQ-5 score and pre-bronchodilator FEV₁ by visit will be provided. Lastly, bar graphs of the LS means and CIs for Week 24 for ACQ-5 score and pre-bronchodilator FEV₁ will be provided.

Lastly, a sensitivity analysis with a different method of handling pre-bronchodilator FEV₁ measurements confounded by systemic corticosteroid use will be performed. Pre-bronchodilator FEV₁ measurements collected from systemic corticosteroid start date to systemic corticosteroid end date + 14 days will be excluded in order to reduce the confounding effect of systemic corticosteroids. If the number of subjects overall with a missing change from baseline is < 5%, then only ANCOVA without MI will be performed. If the number of subjects overall with a missing change from baseline value is \geq 5%, ANCOVA with MI and MMRM with MI will be performed.

ACQ-5 score, pre-bronchodilator FEV₁, post- bronchodilator FEV₁, and AM PEF data will also be presented in by-subject data listings.

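### If the unstructured MMRM fails and compound symmetry or AR(1) is used instead, the Week 24 standard error is wrong whenever residual variance changes over the visits

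*SAP*

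**What the plan says.** SAP 8.3.2.1 (Change from Baseline to Week 24 Endpoints) states that the MMRM will "be performed using a restricted maximum-likelihood (REML)-based approach and an unstructured covariance structure to model within-subject error". Treatment contrasts are reported as differences in LS means, and "p-values with Kenward-Roger adjustment (Kenward, 1997) will be provided for comparison for each GB001 group versus placebo".

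For non-convergence, "the following will be considered to enable model convergence: 1) use of maximum likelihood estimation instead of REML; and/or 2") that "a compound symmetric or first-order autoregressive covariance structure will be utilized", the choice between them being "based on the covariance structure converging to better fit as determined based on Akaike's information criterion (Akaike, 1973"). No heterogeneous-variance structure and no empirical (sandwich) variance is named.

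The MMRM has a supporting role. When fewer than 5% of change values are missing, ANCOVA without MI is primary: "As a sensitivity analysis, mixed-effects model with repeated measures (MMRM) without MI will also be performed". When 5% or more are missing, ANCOVA with MI is primary: "As sensitivity analyses, MMRM with MI, ANCOVA without MI, and MMRM without MI will also be performed". Table 1 of the SAP shows the same roles for ACQ-5, pre-bronchodilator FEV1 and AM PEF. Post-bronchodilator FEV1 has no MMRM.

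**The concern.** As ordinarily defined, compound symmetry and AR(1) each have one variance parameter shared by all visits. The reported contrast is at Week 24 only. If residual variance at Week 24 differs from the variance pooled over visits, the fitted SE for that contrast is wrong. AIC cannot help, because both candidates share the restriction. Kenward-Roger allows for covariance parameters being estimated, not for the wrong structure having been chosen.

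A variance that rises over the visits is plausible. The model adjusts for baseline and baseline-by-visit, so residual variance at visit t is proportional to 1 - r(t)², where r(t) is the correlation with baseline. If that correlation weakens with time, residual variance rises, and Week 24 is the visit furthest from baseline. For illustration, assume r falls from 0.8 to 0.6. The relative SDs are then √(1 - 0.64) = 0.6 and √(1 - 0.36) = 0.8, a ratio of 1.33.

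At stake is the worth of a robustness check: an MMRM interval that is too narrow would give false reassurance about three secondary endpoints.

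**Working it through.** **The plan's own figure.** The documents give no SD, SE or power for the MMRM endpoints. The only power statement (SAP 2.5; Protocol 9.2) is for the primary binary endpoint, and it reproduces. Evaluable n per arm = 120 × 0.92 = 110.4. OR = (0.102/0.898)/(0.25/0.75) = 0.341, so ln OR = -1.077. Variance = [1/(0.25 × 0.75) + 1/(0.102 × 0.898)]/110.4 = 0.1472, so SE = 0.3837. Power = Φ(1.077/0.3837 - 1.96) = 80.1%. What carries over to this point is about 110 evaluable subjects per arm.

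**Inputs from the documents.** SAP 2.2 gives seven post-baseline visits (Weeks 2, 4, 8, 12, 16, 20, 24), used here for ACQ-5 and AM PEF. Protocol 8.1.3 omits spirometry at Visit 3 (Week 2), which leaves six for FEV1. The unstructured matrix has 7 × 8/2 = 28 or 6 × 7/2 = 21 parameters.

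**Assumed input.** Residual SD is linear in weeks between Week 2 and Week 24.

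**Formulas (large sample, complete data, model-based SE).** The true variance of the Week 24 difference is 2σ²(24)/n; the fitted model reports 2σ²(fit)/n. So

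- SE ratio λ = √[σ²(fit)/σ²(24)]
- true size of the nominal 5% test = 2[1 - Φ(1.96λ)]
- compound symmetry: σ²(fit) tends to the mean of the visit variances
- AR(1): σ²(fit) is the value minimising k ln σ² + ln|R(ρ)| + tr(R(ρ)⁻¹Σ)/σ², for k visits and true covariance Σ.

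**Worked case, compound symmetry, SD 0.7 to 0.9.** Visit variances are 0.490, 0.516, 0.569, 0.626, 0.684, 0.746 and 0.810.

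- Seven visits: mean 0.634; λ = √(0.634/0.810) = 0.885; size 8.3%.
- Six visits (without Week 2): mean 0.658; λ = 0.902; size 7.7%.

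**All cases, CS and AR(1) together.** For AR(1) the true correlation was taken as exchangeable 0.6, AR(1) 0.8, or a blend of the two.

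| Assumed SD, Week 2 to 24 | Seven visits (ACQ-5, AM PEF) | Six visits (FEV1) |
|---|---|---|
| 0.7 to 0.9 | SE 11-12% too small, size about 8% | about 10% too small, 7.7% |
| 0.6 to 1.0 | 19-20% too small, 11-12% | about 17% too small, about 10.4% |
| constant | no error, 5.0% | no error, 5.0% |
| 0.9 to 0.7 | about 16% too large, about 2.3% | about 13% too large, about 2.6% |

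**Cross-checks.** The same calculation with 0-8% dropout, over both visit schedules, gave λ of 0.90-0.92 when the last SD is 1.2 times the first, and 0.82-0.84 at 1.5 times. A simulation (four arms of 110, seven visits, complete data, 4000 runs, REML) took the better of CS and AR(1). They have equal parameter counts, so likelihood and AIC agree. At SD ratios 1.2, 1.5 and 2.0 the SE ratios were 0.93, 0.83 and 0.76, and the type I error was 7.1%, 10.5% and 14.0%. The unstructured model stayed at 5.1-5.5%.

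**The case against.** The strongest reply is that several things must all happen, and none is established. The unstructured model must fail, which is unlikely with 21-28 covariance parameters and about 480 subjects. The analyst must then go past ML with the unstructured matrix, which is listed first and may be used alone. Finally, the residual variance must change over the visits, and no section gives an SD by visit. This stands, and it is why the point is minor.

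Three stronger readings are tempting, and the documents support none of them:

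- **That compound symmetry or AR(1) follows automatically on failure.** The SAP words the options as things to be considered, joined by and/or.
- **That the fallback intervals are always too narrow.** The direction depends on the variance pattern: flat variance gives no error, and falling variance gives intervals that are too wide.
- **That secondary endpoint conclusions are at risk.** ANCOVA is primary for each endpoint, and the dose-response analysis for ACQ-5 and FEV1 uses the primary method. By-visit summaries and the ANCOVA SE would sit beside the MMRM result, so a reader could see growing variance or an implausibly narrow interval.

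It is also fair to say that the SAP does not state which variance estimator applies under the fallback. That it is model-based is inferred from the Kenward-Roger specification and from the absence of any sandwich option.

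What remains is that the named structures cannot represent a separate Week 24 variance, and that the and/or wording leaves the sequence to be settled at analysis.

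**Conclusion.** The point holds in conditional form and is a low-priority improvement. If compound symmetry or AR(1) is used with model-based errors, the Week 24 SE is wrong to the extent that residual variance changes over the visits. Over the assumed patterns, the error runs from about 20% too small (SD 0.6 to 1.0, seven visits) through zero (constant SD) to about 16% too large (SD 0.9 to 0.7, seven visits). The corresponding true size runs from nearly 12% down to about 2.3%. These figures rest on assumed linear SD paths and large-sample limits. Only the MMRM sensitivity analyses of ACQ-5, pre-bronchodilator FEV1 and AM PEF are affected, including the FEV1 sensitivity analysis that excludes values around systemic corticosteroid use when its MMRM is triggered.

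**What to change.** Replace the non-convergence sentence in SAP 8.3.2.1 with a fixed order:

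1. ML with the unstructured matrix.
2. Heterogeneous Toeplitz, then heterogeneous AR(1), then heterogeneous compound symmetry, taking the first that converges.
3. Homogeneous AR(1) or compound symmetry only as a last resort.

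Add that the empirical (sandwich) variance is used whenever the structure is not unstructured. The heterogeneous structures free the Week 24 variance, although they were not simulated here. The sandwich variance guards the Week 24 SE in either direction, including at the last step.

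The cost is one sentence and the loss of the Kenward-Roger adjustment in those fits, which is negligible at about 110 evaluable subjects per arm. Design, data collection and the primary analyses do not change.

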8.3.3.2. Additional Markers of Asthma Control

8.3.3.2.1. Change from Baseline in Daily Rescue Medication Use, Daily Asthma Symptom Scores, and Awakening at Night Due to Asthma Symptoms Requiring Rescue Medication Use

Rescue medications include the study-provided salbutamol/albuterol or any other short-acting bronchodilator. All rescue medication use is to be captured in an eDiary.

Change from baseline to Week 24 in daily rescue medication use, daily asthma symptoms scores, and awakening at night due to asthma symptoms requiring rescue medication use will be analyzed using an ANCOVA model without MI. Covariate adjustment is the same as the primary endpoint except that baseline pre-bronchodilator FEV₁ will be replaced with baseline rescue medication use, baseline daily symptom score, or baseline awakening at night due to asthma symptoms requiring rescue medication use, depending on the endpoint of interest.

Daily rescue medication use is collected as the number of puffs during the past 24 hours. The baseline rescue medication value is defined as the mean number of puffs over the last 7 days of the Run-in including the value on Day 1 and Week 24 is defined as the mean number of puffs over the last 7 days prior to Week 24 including the value on the day of the Week 24 visit. Similarly, the value at all other post-baseline visits is defined as the mean number of puffs over the last 7 days prior to that visit including the day of the visit.

Daily asthma symptom score over the previous 24 hours is assessed by subjects using a 6-point scale, with higher values indicating greater symptom severity, and is captured in the same eDiary as rescue medication use. Subjects also record the number of times they had awakening at night due to asthma symptoms requiring rescue medication use in this same eDiary.

Baseline and post-baseline visit values for daily symptom scores and awakening at night are defined as for daily rescue medication use. In order for the mean to be calculated at a visit, 4 out of the 7 days must have non-missing values. If < 4 of 7 days are available, the mean is considered missing.

Actual values and change from baseline values will be summarized by visit. Differences in means, SEs, and corresponding 95% CIs constructed from ANOVA models adjusting for treatment group only will also be presented. These data will also be presented in by-subject data listings.

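### By-visit treatment differences come from treatment-only ANOVA. Rescue use, symptom score and night awakening have no other between-group comparison before Week 24, so their intervals are somewhat wider than they need be (minor)

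*SAP*

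**What the plan says.** **By-visit tables.** SAP 8.3.2.1 covers ACQ-5, pre- and post-bronchodilator FEV1 and AM PEF. After promising summaries of actual values and changes by visit, it adds: "Differences in means, SEs, and corresponding 95% CIs constructed from analysis of variance (ANOVA) models adjusting for treatment group only will also be presented". SAP 8.3.3.2.1 covers daily rescue use, daily symptom score and night awakening: "Actual values and change from baseline values will be summarized by visit", and then "Differences in means, SEs, and corresponding 95% CIs constructed from ANOVA models adjusting for treatment group only will also be presented". Neither sentence lists p-values or says whether the ANOVA differences are for actual values, changes or both.

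**Week 24 models.** For the secondary endpoints, "Each secondary endpoint of change from baseline to Week 24 will be analyzed using ANCOVA models". The covariates are those of the primary model in SAP 8.3.1: treatment, ICS dose at randomization, region, baseline pre-bronchodilator FEV1 and baseline ACQ-5. "Covariate adjustment will be the same as for the primary endpoint for ACQ-5 score" and pre-bronchodilator FEV1; AM PEF and post-bronchodilator FEV1 substitute their own baseline. For the diary endpoints, "Covariate adjustment is the same as the primary endpoint except that baseline pre-bronchodilator" FEV1 gives way to the endpoint's own baseline.

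**MMRM.** SAP 8.3.2.1 plans one for ACQ-5, pre-bronchodilator FEV1 and AM PEF, with ICS dose, region, treatment-by-visit, baseline and baseline-by-visit terms. Table 1 plans none for the diary endpoints.

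**The concern.** SAP 8.2 makes the ICS stratification factor a covariate in all efficacy analyses unless otherwise stated. The two ANOVA sentences do state otherwise, but without a reason, and they also drop the baseline and region terms that the same endpoints carry at Week 24.

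This is a dose-ranging trial (Protocol 4.3), so the by-visit tables will be read for when an effect appears and at which dose. For the three diary endpoints nothing else compares the groups before Week 24. A less efficient model there gives wider intervals and leaves any chance baseline imbalance unadjusted, or only partly removed by subtraction. The Week 24 row will also show a second estimate beside the designated ANCOVA, and the by-visit text does not say how the two relate.

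**Working it through.** **Inputs**
- From SAP 2.5: about 120 per arm, 8% dropout, event proportions 25% and 10.2%, two-sided 0.050, 80% power.
- Assumed, because the documents give neither: the baseline-to-visit correlation ρ (0.5, 0.7 and 0.8, with a wider range of 0.3 to 0.9) and equal variance at baseline and at the visit.

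**1. The plan's own figure.** OR = (0.102/0.898)/(0.25/0.75) = 0.341, the stated 66% reduction in odds. On the log-odds scale, n = (1.960 + 0.842)² × [1/(0.25×0.75) + 1/(0.102×0.898)] / (ln 0.341)² = 110.05, so 111 per arm, and 111/0.92 gives 121 against the stated 120. Power at 120 × 0.92 = 110.4 per arm is 80.1%. The figure reproduces and implies about 110 evaluable per arm. It concerns only the binary primary endpoint; no figure is given for the by-visit tables.

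**2. Variance per subject, unit variance at each visit**
- Treatment-only ANOVA on change: 2(1 − ρ)
- Treatment-only ANOVA on actual value: 1
- ANCOVA with own baseline (same treatment difference for change or actual value): 1 − ρ²

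The interval-width ratio to ANCOVA is therefore √(2/(1 + ρ)) for change and 1/√(1 − ρ²) for actual values.

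**3. Results**

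| ρ | Change: ANOVA/ANCOVA width | Narrowing if adjusted | Actual value: ANOVA/ANCOVA width |
|---|---|---|---|
| 0.3 | 1.240 | 19.4% | 1.048 |
| 0.5 | 1.155 | 13.4% | 1.155 |
| 0.7 | 1.085 | 7.8% | 1.400 |
| 0.8 | 1.054 | 5.1% | 1.667 |
| 0.9 | 1.026 | 2.5% | 2.294 |

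**4. Absolute size with 110 per arm.** The half-width is 1.96 × √(2V/110) in SD units. For change at ρ = 0.5, ANOVA gives 0.264 (V = 1) and ANCOVA 0.229 (V = 0.75). At ρ = 0.7 they give 0.205 (V = 0.60) and 0.189 (V = 0.51).

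**5. Simulation check.** Four arms of 110, adjusting for baseline, ICS dose and region, gave ratios for change of 1.23, 1.15, 1.08 and 1.02 at ρ = 0.3, 0.5, 0.7 and 0.9, and 1.04, 1.15, 1.40 and 2.29 for actual values. If ICS dose explained 5% of the residual variance (assumed), the change ratios became 1.27, 1.18, 1.11 and 1.05, so the stratum adds about 2 to 3%. Baseline ACQ-5, the further covariate for the diary endpoints, was not modelled.

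**6. Planned between-group comparisons**

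| Endpoint | Before Week 24 | At Week 24 |
|---|---|---|
| Rescue use, symptom score, night awakening | Unadjusted ANOVA only | ANCOVA without MI |
| ACQ-5, pre-bronchodilator FEV1, AM PEF | Unadjusted ANOVA; MMRM fitted, but reporting of earlier contrasts not stated | ANCOVA (with MI if missing ≥ 5%) and MMRM |
| Post-bronchodilator FEV1 | None possible: one post-baseline timepoint | ANCOVA (with MI if missing ≥ 5%) |

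The Week 24 row of the by-visit tables adds an unadjusted ANOVA difference for all of them.

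**The case against.** The case for leaving the tables alone is substantial. They are supplementary: no p-values are listed, treatment-only ANOVA has no column in Table 1, and every named endpoint has a covariate-adjusted Week 24 analysis. Raw differences beside raw means are a legitimate display. The three endpoints most affected are exploratory.

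A reader might infer more than the documents support:
- **That the trial's conclusions or power suffer.** They do not. SAP 2.5 powers only the binary primary endpoint, and no effect size is given for these outcomes, so the widths cannot be turned into a power loss for any planned test.
- **That the differences are biased.** Randomization protects them by design; missing data and chance imbalance aside, the cost is precision.
- **That baseline is ignored.** A change score subtracts it, so the loss for change is small when ρ is high.
- **That the 40% and 67% figures are the size of the problem.** They apply to actual values only, and the text does not settle whether the ANOVA covers those.
- **That nothing else describes time course.** The MMRM carries a treatment-by-visit term for three endpoints, SAP 8.3.2.2 has an adjusted Cox model with Kaplan-Meier summaries, and SAP 8.3.2.3 analyses exacerbation rates by period.

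Nor does adjusting each visit remove the second Week 24 estimate for the secondary endpoints. With 5% or more missing, their designated ANCOVA uses MI, and the 8% assumed dropout makes that plausible.

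All of this limits the weight of the point. None of it gives a reason to leave the diary endpoints unadjusted before Week 24.

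**Conclusion.** The point holds as a minor improvement in efficiency. It is strongest for rescue use, symptom score and night awakening, where the treatment-only ANOVA is the sole comparison before Week 24. For ACQ-5, pre-bronchodilator FEV1 and AM PEF it is mainly a reporting gap, since the better model is already planned. Post-bronchodilator FEV1 is unaffected before Week 24.

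The size for change from baseline is an interval about 5% to 15% wider over ρ = 0.8 to 0.5, and more for actual values at ρ above 0.5 if the ANOVA is applied to them. These figures rest on the assumed ρ and equal variances. Week 24 inference, the primary analysis and the sample size do not change.

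**What to change.** - **SAP 8.3.3.2.1:** at each visit, replace the treatment-only ANOVA with the covariates already specified for Week 24 (own baseline, ICS dose at randomization, region, baseline ACQ-5). As that Week 24 ANCOVA uses no MI, the Week 24 row should then match it.
- **SAP 8.3.2.1:** for ACQ-5, pre-bronchodilator FEV1 and AM PEF, report the MMRM treatment-by-visit LS mean differences and 95% CIs at every visit, or fit each endpoint's Week 24 ANCOVA covariates by visit. Post-bronchodilator FEV1 needs no by-visit change.
- **Both sections:** keep raw means and SDs as descriptive columns, say whether differences are for change, actual values or both, and state that the designated Week 24 analysis takes precedence.

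The cost is a few sentences of SAP wording and a changed model statement. No new data or patients are needed.
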